9.4.4 Patient-reported outcomes

The following patient-reported outcomes (PRO) questionnaires will be assessed: the NSCLC-SAQ, EORTC QLQ-C30, the FACT-GP5, PRO-CTCAE and the EQ-5D-5L. Of these the NSCLC-SAQ, EORTC QLQ-C30, and FACT-GP5 will be analyzed by cohort (A and B) to assess the secondary objectives. The other questionnaires may be evaluated in exploratory analyses.

The FAS will be used for analyzing PRO data.

Scoring of PRO data and methods for handling of missing items or missing assessments will be according to the scoring manual and user guide for each respective participant questionnaire (Aaronson et al 1993, Fayers et al 2001, McCarrier et al 2016). No imputation procedures will be applied for missing items or missing assessments.

Time to definitive deterioration in the NSCLC-SAQ total score is the primary PRO variable of interest. Time to definitive deterioration (TTDD) in physical functioning (PF)of the QLQ-C30 is the secondary PRO variable of interest.

The time to definitive 10-point deterioration for SAQ total score (TS) or C30 PF, respectively, is defined as the time from the date of enrollment to the date of meaningful worsening. For the TS it is defined as at least 1-point absolute increase in score from baseline (worsening), and for PF it is defined as at least 10-point absolute decrease in score from baseline (worsening), with no later improvement above these thresholds during the course of the treatment or until death

due to any cause (within 3 weeks of the last assessment). If a participant has not had an event, time to definitive deterioration will be censored at the date of the last adequate PRO assessment. Only assessments collected while the participant is on treatment and at the end of treatment visit will be included in the PRO TTDD. Participants with no baseline data or no post-baseline data will be censored at baseline.

The distribution of time to definitive deterioration will be summarized using the Kaplan-Meier method, and the Kaplan-Meier curves, medians, and two-sided 95% confidence intervals of the medians will be presented. Additionally, time to definitive deterioration with different cut-off definitions for deterioration may be specified in the SAP as deemed appropriate.

Descriptive statistics will be used to summarize the scores, as well as change from baseline, of the EORTC QLQ-C30, EQ-5D-5L,NSCLC-SAQ and PGIS-NSCLC at each scheduled assessment and to EOT. Additionally, change from baseline scores will assess SAQ total score, pain and fatigue domains, and cough, dyspnea and appetite loss items; C30 GHS/QoL and functional domains as well as symptom items/domains and financial problems item. Participants with an evaluable baseline score and at least one evaluable post-baseline score during the on-treatment period will be included in the change from baseline analyses.

The number of participants completing each PRO and the number of missing or incomplete assessments will be summarized by cohort for each scheduled assessment timepoint. No formal statistical tests will be performed for PRO data and hence no multiplicity adjustment will be applied.

9.5 Exploratory endpoint(s)/estimand(s) analysis

Further details for the analysis of exploratory endpoints might be provided in the statistical analysis plan.

9.5.1 Biomarkers

The statistical goals of exploratory biomarker analysis should be considered as promoting the generation of new scientific hypotheses and are exploratory in nature.

There may be circumstances when a decision is made to stop sample collection, or not perform or discontinue their analysis due to either practical or strategic reasons (e.g., issues related to the quality and/or quantity of the samples or issues related to the assay). Under such circumstances, the number of samples may be inadequate to perform a rigorous data analysis and the available data will only be listed and potentially summarized.

9.5.1.1 Outline of the data analysis

The proposed data analysis will be aligned with the exploratory biomarker objectives of the protocol:

- To assess CCI
- To assess CCI

To explore the **CC** To assess the relationship CCI

9.5.1.2 Data analysis principles

The FAS will be used for all biomarker analyses unless otherwise specified.

Depending on the endpoint of interest, graphical displays such as box plots or strip plots may be used to assess the relationship of different biomarkers with clinical benefit. These may be separated by cohort and include either baseline or change from baseline values, where applicable.

For continuous markers, baseline and change from baseline (absolute change, percent change and fold change) at each time point will be summarized in tables that include sample size, mean, standard deviation, CV%, median, minimum and maximum. For fold change from baseline, geometric mean and geometric CV% will also be included. For categorical markers such as mutation status, 2×2 contingency tables may be used to assess the relationship with clinical benefit and/or Kaplan-Meier curves may be generated given the number of events warrant such an assessment.

If additional analyses are needed to be performed after the completion of the end-of-study clinical study report (CSR), they will be documented in separate reports. The data analysis will be described in an addendum of the statistical analysis plan (SAP) or in a stand-alone analysis plan document, as appropriate.

9.5.2 **Pharmacokinetics**

Pharmacokinetic data from this study will be analyzed using population PK approach, which may include exploring the effect of covariates on PK, if data allow. The PK data from this study may be combined with similar data from other studies and explored using population PK. Exploratory analyses may also be conducted to identify possible relationships of JDQ443 exposure (e.g., Cmax, Cmin or AUC) with PD markers, clinical efficacy (ORR, PFS, and OS) or safety variables as appropriate. The results of such exploratory analyses will be reported separately from the CSR.

9.6 (Other) Safety analyses

Not applicable

9.7 Other analyses

Not applicable

9.8 Interim analysis

The planned interim analyses will be performed separately for each of the two cohorts. In case the interim analysis (IA) of the two cohorts happens at a similar time, the IA will be reported together.

9.8.1 Primary endpoint: ORR in cohort A

One IA is planned for cohort A based on approximately the first 30 evaluable participants. Evaluable participants are defined as enrolled participants who have been followed for at least two tumor assessments or have discontinued the study earlier. The primary intent of the interim analysis is to stop the cohort early for lack of efficacy (futility).

The decision whether to continue or stop enrollment and/or treatment will be based on the predictive probability of success (PPoS). PPoS is the predictive probability of a positive conclusion of the study (regarding cohort A) if it continued beyond the interim analysis (i.e., until the final analysis), given the interim observed data (x) and successes among n participants.

PPoS = Prob[Final observed ORR \geq | x, n |

A minimally informative Beta distribution prior (Neuenschwander et al 2008) with prior mean equal to will be used, i.e., the prior distribution will be Beta (CC) for the PPoS calculations at the interim analysis.

The cohort will be stopped for futility at the interim analysis if the observed ORR is \leq corresponding to 9 or less responders (at least responders out of 30 participants are required for the study to proceed). If the futility criterion is met, the predictive probability of observing a success in the future based on the existing data will be \leq %.

All evaluable participants in cohort A at the time of the data cut-off for the interim analysis will be used.

If futility is concluded, the enrollment of participants in the cohort will be stopped. The enrollment in cohort B will continue, if applicable.

Table 9-2 provides the PPoS at the primary analysis based on different numbers of responders observed at the interim analysis. For CCI responders, PPoS exceeds % and the cohort will continue after the interim analysis.

Table 9-2 PPoS at the primary analysis based on various numbers of responders observed at the IA

Responders at IA out of 30 evaluable participants	Predictive probability of success (%)
5	CCI
6	CCI
7	CCI
8	CCI
9	CCI
10	CCI
11	CCI
12	CCI

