4.1 Overall design

This is a non-randomized, open-label, single-arm, multicenter, phase II study evaluating the antitumor activity and safety of JDQ443 single-agent as first-line treatment for participants with locally advanced or metastatic KRAS G12C-mutated NSCLC (Figure 1-1).

The study will have 2 non-comparative cohorts that will enroll approximately 120 participants in parallel according to the following characteristics:

- **Cohort A:** participants whose tumors harbor a KRAS G12C mutation and a PD-L1 expression < 1%, regardless of STK11 mutation status (N=90).
- Cohort B: participants whose tumors harbor a KRAS G12C mutation, a PD-L1 expression $\geq 1\%$ and an STK11 co-mutation (N=30).

The sample size of cohorts A and B was determined based on the estimated frequency of the molecular profile required to meet eligibility criteria for each cohort: the prevalence of PD-L1 expression <1% is estimated as around 40% in patients with KRAS G12C- mutated NSCLC, whereas STK11 co-mutations are found in around 12-15% of these patients (Skoulidis et al 2015, Skoulidis and Heymach 2019, Aredo et al 2019, Ricciuti et al 2021 and Skoulidis et al 2021). Due to the differences in terms of sample size, the antitumor activity of JDQ443 will be assessed as primary objective in cohort A, and as a key secondary objective in cohort B.

The statistical analyses will be performed separately for each of the two cohorts. For both cohort A and cohort B, an interim analysis is planned to stop early for lack of efficacy (futility). The interim analysis in cohort A will be performed based on ORR in approximately the first 30 participants enrolled who have been followed for at least two tumor assessments or have discontinued the study earlier. In cohort B, the interim analysis will be based on approximately

Amended Protocol Version No.01 (Clean)

the first 15 participants enrolled who have been followed for at least two tumor assessments or discontinued the study earlier.

Details are described in Section 9.8.

JDQ443 treatment may be continued beyond initial disease progression as per RECIST 1.1 by BIRC if, in the judgement of the Investigator, there is evidence of clinical benefit, and the participant wishes to continue on the study treatment (for additional details please refer to Section 6.1.4.1).

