4.6 Purpose and timing of interim analyses/design adaptations

One interim futility analysis per cohort is planned to assess ORR independently in each cohort when approximately 30 and 15 participants, in cohort A and cohort B, respectively, have been enrolled and followed for 2 tumor assessments or have discontinued the study earlier, with the objective to allow an early assessment of the antitumor activity of JDQ443, as well as to allow the discontinuation of the respective cohort in case the futility criteria are met. For further details please refer to Section 9.8.

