9.3.2 Statistical model, hypothesis, and method of analysis

The primary analysis will be performed on the FAS. The primary efficacy endpoint ORR will be estimated and the exact 95% confidence interval (CI) (Clopper and Pearson 1934) provided.

Treatment with JDQ443 will be considered to have clinically relevant efficacy if an ORR of CCI (per RECIST 1.1 by BIRC assessment) is observed with the lower bound of the 95% confidence interval CCI. The following statistical hypotheses will be tested:

 H_0 : ORR CCI vs. H_1 ORR $\geq 35\%$.

The tests will be performed based on the exact confidence interval for ORR using a one-sided α =0.025 level. The null hypothesis will be rejected if the lower bound of the two-sided 95% exact CI is \geq 35%.

An interim analysis for futility will be performed to assess ORR in approximately the first 30 evaluable participants. Evaluable participants are defined as enrolled participants who have been followed for at least two tumor assessments or have discontinued the study earlier (see Section 9.8).

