One interim analysis for futility to assess ORR by BIRC independently in each cohort is planned, when approximately the first 30 (cohort A) and approximately the first 15 participants (cohort B) have been enrolled and followed for at least 2 tumor assessments or have discontinued the study treatment earlier. The primary intent of the interim analyses is to allow an early assessment of the antitumor activity of JDQ443 and to discontinue the respective cohort early if lack of efficacy (futility) is observed. In case the IA of the two cohorts occurs at a similar time, the IAs will be reported together.

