2.15.1 Primary endpoint: ORR in cohort A

One IA is planned for cohort A based on approximately the first 30 evaluable participants. Evaluable participants are defined as enrolled participants who have been followed for at least two tumor assessments or have discontinued the study treatment earlier. The primary intent of the interim analysis is to stop the cohort early for lack of efficacy (futility).

The decision whether to continue or stop enrollment and/or treatment will be based on the predictive probability of success (PPoS). PPoS is the predictive probability of a positive conclusion of the study (regarding cohort A) if it continued beyond the interim analysis (i.e., until the final analysis), given the interim observed data (x) and successes among n participants.

$$\text{PPoS} = \text{Prob}[\text{Final observed ORR} \geq \text{[REDACTED]} x, n]$$

A minimally informative Beta distribution prior ([Neuenschwander et al 2008](#)) with prior mean equal to [REDACTED] will be used, i.e., the prior distribution will be Beta [REDACTED] for the PPoS calculation the interim analysis.

The cohort will be stopped for futility at the interim analysis if the observed ORR is \leq [REDACTED] corresponding to 9 or less responders (at least [REDACTED] responders out of 30 participants are required for the study to proceed). If the futility criterion is met, the predictive probability of observing a success in the future based on the existing data will be [REDACTED]

All evaluable participants in cohort A at the time of the data cut-off for the interim analysis will be used.

If futility is concluded, the enrollment of participants in the cohort will be stopped. The enrollment in cohort B will continue, if applicable.

[Table 2-9](#) provides the PPoS at the primary analysis based on different numbers of responders observed at the interim analysis. For [REDACTED] responders, PPoS exceeds [REDACTED] and the cohort will continue after the interim analysis.

Table 2-10 PPoS at the primary analysis based on various numbers of responders observed at the IA

Responders at IA out of 30 evaluable participants	Predictive probability of success (%)
5	[REDACTED]
6	[REDACTED]
7	[REDACTED]
8	[REDACTED]
9	[REDACTED]
10	[REDACTED]

Responders at IA out of 30 evaluable participants	Predictive probability of success (%)
11	[REDACTED]
12	[REDACTED]

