2.15.2 Key secondary endpoint: ORR in cohort B

One interim analysis is planned for cohort B based on approximately the first [REDACTED] participants. Evaluable participants are defined as enrolled participants who have been followed for at least two tumor assessments or have discontinued the study earlier. The primary intent of the interim analysis is to stop the cohort early for lack of efficacy (futility).

The decision whether to continue or stop enrollment and/or treatment will be based on the PPoS.

$$\text{PPoS} = \text{Prob}[\text{Final observed ORR} \geq [REDACTED] | x, n]$$

A minimally informative Beta distribution prior (Neuenschwander et al 2008) with prior mean equal to 20% will be used, i.e., the prior distribution will be Beta (0.25, 1) for the PPoS calculations at the interim analysis.

The cohort will be stopped for futility at the interim analysis if the observed ORR is [REDACTED] corresponding to [REDACTED] or less responders (at least [REDACTED] responders out of [REDACTED] participants are required for the cohort to proceed). If the futility criterion is met, the predictive probability of observing a success in the future based on the existing data will be [REDACTED]

All evaluable participants in the cohort at the time of the data cut-off for the interim analysis will be used.

If futility is concluded, the enrollment of participants in the cohort will be stopped. The enrollment in cohort A will continue, if applicable.

Table 2-10 provides the PPoS at the primary analysis based on different numbers of responders observed at the interim analysis. For [REDACTED] or more responders, PPoS exceeds [REDACTED] and the cohort enrollment will continue after the interim analysis.

Table 2-11 PPoS at the final analysis based on various numbers of responders observed

Responders at IA out of [REDACTED] participants	Predictive probability of success (%)
1	[REDACTED]
2	[REDACTED]
3	[REDACTED]
4	[REDACTED]
5	[REDACTED]
6	[REDACTED]

3 Sample size calculation

A total of 120 participants will be enrolled in 2 separate cohorts that will recruit in parallel: 90 in cohort A and 30 in cohort B, if none of the cohorts is stopped for futility at the time of the corresponding interim analysis.

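### The futility set is defined two ways: leaving the study (protocol, SAP cohort B) or leaving study treatment (SAP 1.1 and cohort A); the protocol wording drops some certain non-responders

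*Protocol*

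**What the plan says.** One futility look is planned per cohort, at about 30 participants in cohort A and 15 in cohort B. Cohort A stops at 9 or fewer responders out of 30. The matching ORR and predictive-probability thresholds are redacted.

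**Wording based on leaving the study**
- Protocol 4.1: "approximately the first 30 participants enrolled who have been followed for at least two tumor assessments or have discontinued the study earlier"
- Protocol 4.6: "followed for 2 tumor assessments or have discontinued the study earlier"
- Protocol 9.3.2: "followed for at least two tumor assessments or have discontinued the study earlier"
- Protocol 9.4.1.1, 9.8.1 and 9.8.2 use the same criterion. In full, 9.8.1 reads: "Evaluable participants are defined as enrolled participants who have been followed for at least two tumor assessments or have discontinued the study earlier"
- SAP 2.15.2, cohort B: "have discontinued the study earlier"

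**Wording based on leaving study treatment**
- SAP 1.1, both cohorts: "followed for at least 2 tumor assessments or have discontinued the study treatment earlier"
- SAP 2.15.1, cohort A: "have discontinued the study treatment earlier"

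Cohort A therefore differs between protocol and SAP, and cohort B differs within the SAP. The SAP says it is based on protocol version 00. The change list for Amendment 01 mentions no change to this definition, so it does not explain the difference.

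**The concern.** Protocol 7.2 and 10.2.2 separate the two events. Leaving the study means stopping treatment and also all further assessments or follow-up. Leaving treatment means stopping the drug while agreeing to follow-up. The first group is contained in the second, so the protocol's evaluable set is the smaller one.

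The participants in the gap are an ordinary group. After progression confirmed by BIRC, treatment stops and no more scans are required, unless treatment continues beyond progression (Protocol 8.4.1). The participant then moves on to survival follow-up (Protocol 7.1.3). If this happens at the first scan, that person has one assessment and is still in the study. Such a participant is evaluable under SAP 2.15.1, but on a literal reading of the protocol is not evaluable until death, withdrawal or loss to follow-up. A confirmed response is impossible, so only non-responders are removed. The bias is always towards a higher interim ORR and a weaker futility rule. What is at stake is whether a cohort with too little activity goes on enrolling.

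**Working it through.** **Inputs from the documents.** Cohort A: interim at 30, stop at 9 or fewer (Protocol 9.8.1); 90 participants in total; success if the exact 95% lower bound is at least 35% (Protocol 9.3.2). No interim result is stated unredacted, so there is no plan figure to reproduce in full.

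**Partial check of the final rule.** The Clopper-Pearson lower bound at n = 90 is 0.3396 for 40 responders and 0.3502 for 41. Success therefore needs at least 41/90 (45.6%). With no futility look, this gives one-sided alpha 2.48% at a true ORR of 35% and power 82.9% at 50%.

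**Assumption.** The documents do not give e, the share of participants who are off treatment, still in the study and have fewer than two scans. I use 5% and 10%.

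**(a) One data snapshot.** Suppose 30 participants have reached the interim point, 9 have responded and 3 early progressors are in survival follow-up.
- Counting everyone: 9/30 = 30.0%.
- Literal protocol wording: 9/27 = 33.3%.

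The responder count is the same; the denominator changes, and with it the predictive probability of success (PPoS). To size that change, assume a Beta(m/(1−m), 1) prior, the form shown for cohort B in SAP 2.15.2, with assumed means m of 35% to 50%, and success at 41/90. Then PPoS = P(Y ≥ 41 − 9), where Y is beta-binomial on the 90 − n participants still to come, with parameters m/(1−m) + 9 and 1 + n − 9.
- n = 30, 60 to come: 1.8% to 2.3%.
- n = 27, 63 to come: 6.4% to 7.7%.
- n = 27, but with the 3 omitted participants still treated as non-responders in the final 90, so 60 to come: 4.2% to 5.1%.

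**(b) Waiting until 30 evaluable participants have accrued.** With true ORR p, the ORR among those counted is q = p/(1 − e), and P(stop) = P(Bin(30, q) ≤ 9).

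| True ORR | e = 0 | e = 5% | e = 10% |
|---|---|---|---|
| 25% | q = 0.250: 80.3% | q = 0.263: 75.3% | q = 0.278: 69.1% |
| 35% | q = 0.350: 35.8% | q = 0.368: 28.3% | q = 0.389: 21.0% |
| 50% | q = 0.500: 2.1% | q = 0.526: 1.0% | q = 0.556: 0.4% |

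**(c) Effect on the final conclusion.** Let K be the number left out while 30 evaluable participants accrue (negative binomial), and r the responders among the 30. Those left out still count as non-responders in the final 90. Then P(success) = Σ P(K) · P(r) · P(Bin(60 − K, p) ≥ 41 − r), summed over r ≥ 10.
- True ORR 50%: 82.2% at e = 0 and 82.8% at e = 10%.
- True ORR 35%: 2.43% at e = 0 and 2.47% at e = 10%, the largest value found.

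**The case against.** **A separate interim plan governs.** SAP 1, 2.1 and 2.15 place the interim details in a separate plan that was not supplied, and it may settle the definition. It would not remove the conflict between the protocol and the SAP, or the one inside the SAP, but it limits what can be said about how the analysis would actually be run.

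**The sets are nested, and the gap is partly self-closing.** Early progressors who die, withdraw or are scanned again become evaluable. This stands: the assumed shares apply only to those still in follow-up with fewer than two scans at the cut-off.

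**The same data might seem to give two different responder counts, or a reversed decision.** A reader might infer either. The first does not follow, because everyone left out is a non-responder. The second cannot be shown, because the PPoS threshold is redacted.

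**The SAP wording might seem to be a complete answer.** It keeps early progressors in. But SAP 2.15.1 also says: "All evaluable participants in cohort A at the time of the data cut-off for the interim analysis will be used". On that rule a recent starter who stops treatment early enters at once, while someone who started the same day and remains on treatment waits for the second scan. Taking participants in enrolment order, as Protocol 4.1 suggests, would limit this; the two statements need reconciling.

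**Unconfirmed responses at the interim might look like a further gap.** They are not one. The BOR rule in SAP 2.6.1 already classes a PR that has not been confirmed as SD, hence as a non-response.

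**Conclusion.** The inconsistency is real and should be corrected. The direction of the bias under the literal protocol wording follows from the definitions alone; its size rests on the assumed 5% to 10% left out. On that assumption the rule loses about 5 to 11 percentage points of stopping probability at a true ORR of 25% (80.3 − 75.3 = 5.0; 80.3 − 69.1 = 11.2), and about 8 to 15 points at 35% (35.8 − 28.3 = 7.5; 35.8 − 21.0 = 14.8).

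A reader might infer that the primary result is at risk. The documents do not support that. The final ORR is analysed on the FAS, the interim can stop only for futility, and the success probability moves by 82.8 − 82.2 = 0.6 points at a true ORR of 50% and never exceeds 2.47% at 35%. The practical consequence is that an insufficiently active cohort is more likely to continue past the interim.

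**What to change.** Adopt one definition for both cohorts in Protocol 4.1, 4.6, 9.3.2, 9.4.1.1, 9.8.1 and 9.8.2, in SAP 1.1, 2.15.1 and 2.15.2, and in the interim plan. Under it, participants who progress, die or stop treatment before the second assessment stay in the denominator as non-responders.

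So that early stoppers do not enter ahead of their contemporaries, take the set in order of treatment start: the first approximately 30 (cohort A) or 15 (cohort B) treated participants who have reached, or would have reached, the second scheduled scan. One workable form is a first dose at least 13 weeks before cut-off, which is the week 12 scan plus the 1-week window in SAP Table 5-4. Other forms would also serve. Say treated rather than enrolled, because SAP 2.2 ties enrolment to signing the main consent. Reconcile the set with the SAP 2.15.1 statement that every evaluable participant at cut-off is used.

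**Cost.** Aligned wording, which can go into the next protocol amendment with its usual approvals (Protocol 10.1.8.1), and matching edits to the SAP and interim plan. No extra scans or visits are needed. The cut-off may fall slightly later than under the SAP wording. Allow for central reading time as well, since scans without local progression are not read on an expedited basis (Protocol 8.4.1).
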